4.4.3.2 Biomarker Research

The investigator will conduct biomarker research on biopsy and blood collected on trial patients. These studies will focus on mechanisms EGFR-TKI resistance and immune correlates.

1. Immunology Correlates

Immunology correlates will be performed by collaborators at the Translational Immuno-Oncology Laboratory Yale University and/or by the Human Immune Monitoring Core at UC Davis as defined in the protocol. The Human Immune Monitoring Core at UC Davis is under the supervision of [name]. [name] laboratory is a world renowned immunology laboratory and has the equipment and expertise to conduct the proposed studies. The Translational Immuno-Oncology Laboratory at Yale University is under the direction of [name] and [name], Ph.D and has been a leader in the translational immuno-oncology of immune checkpoint inhibitors.

a. Biopsy (Biopsy at Baseline and prior to Cycle #3):

- PD-L1 expression by immunohistochemistry at baseline and in repeat biopsy specimens to assess for changes in PD-L1 expression in response to treatment will be conducted by Yale Immuno-Oncology under the direction of [name] using the approved DAKO 22C3 antibody and in addition quantitative IHC assays for PD-L1 if tissue permits. UC Davis may also perform IHC for PD-L1 using the standard DAKO 22C3 antibody.
- Enumeration and changes in immune cell subsets by immunohistochemistry in repeat biopsy specimens in response to treatment will be conducted by Yale Translational Immuno-Oncology.
- Whole exome DNA/RNA next generation sequencing and assessment of mutational load will be performed by the Broad Institute in Boston. The Broad Institute is a world leader in genomic sequencing and analysis.
- RPPA (Reverse Phase Protein Assays) for on-target EGFR pathway inhibition will be performed by Theranostics in collaboration with the [name] lab at UC Davis.

b. Peripheral blood will be collected at relevant time points for enumeration of immune cell subsets and changes in cytokine expression in response to treatment with methods including Flow Cytometry and Luminex Cytokine Assays by the Human Immune Monitoring Core at UC Davis.

Plasma PD-L1 DNA/RNA levels will be assayed by Liquid Genomics in a CLIA certified laboratory.

2. EGFR Correlates

a. Biopsy

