2. In general, the window for each visit is \pm 3 days unless otherwise specified.
3. For women of reproductive potential, a urine or serum pregnancy test will be performed within 72 hours prior to first dose of trial treatment. If urine pregnancy results cannot be confirmed as negative, a serum pregnancy test, performed by the local study site laboratory, will be required. Pregnancy tests (serum and/or urine tests) should be repeated if required by local guidelines.
4. Coagulation factors (PT/INR and aPTT) should be monitored closely throughout the trial for any subject receiving anticoagulant therapy.
5. Laboratory tests for screening are to be performed within 10 days prior to the first dose of trial treatment.
6. After Cycle 1, lab samples can be collected up to 72 hours prior to the scheduled time point. Laboratory results must be known and acceptable prior to dosing.
7. The initial tumor imaging will be performed within 30 days prior to the first dose of trial treatment. Scans performed as part of routine clinical management are acceptable for use as the screening scan if they are of diagnostic quality and performed within 30 days prior to the first dose of trial treatment. On-study imaging will be performed every 6 weeks (42 -7 days) after the first dose of trial treatment or more frequently if clinically indicated. The timing for imaging studies should follow calendar days and should not be adjusted for delays in cycle starts or extension of MK-3475/afatinib cycle frequencies. The same imaging technique should be used in a subject throughout the trial. CT including the chest, abdomen and pelvis or PET-CT is required for the baseline assessment.
8. Provide documentation of the subject's tumor EGFR mutation from a CLIA certified laboratory.
9. MK-3475 can be administered for up to 2 years. For the dose de-escalation and Cohort (Arm) A (concurrent afatinib and MK-3475) both drugs will be administered as outlined in this protocol starting with cycle #1. For cohort B. MK-3475 will be initiated with cycle #1 and afatinib will commence in combination with MK-3475 starting with cycle #3.
10. Tumor biopsy for immune and EGFR biomarker analysis will be performed prior to Cycle 1 of treatment either on archival tissue or fresh biopsy (within 60 days). Repeat biopsy will be performed prior to initiation of cycle 3 (42 days (-7 days))

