7.2.2 Repeat Biopsies for EGFR-mutation Status and Immune Correlates

In all patients following consent, two biopsies will be attempted on study: one prior to initiation of study treatment and one after cycle #2 of treatment before initiation of cycle 3. This will be approximately week 5-6 on study (see study calendar). Patient consent for biopsies will be a study requirement.

Biopsies will be performed by a qualified professional and will be tailored to the available disease targets. Potential biopsies could include image-guided core biopsy, or limited surgical or pulmonary interventional biopsy. Image-guided tumor biopsies will be obtained with the help of the Interventional Radiology or Radiology team by a percutaneous approach or by the assistance of our surgical or pulmonary colleagues. Alternative biopsy techniques (e.g. transbronchial, skin punch biopsy) will be considered if indicated after discussion with the principal investigator. When a core biopsy is performed, it is preferred that a core biopsy system be used to obtain at least 3 core biopsies not less than 22 gauge in diameter and 1 cm in length (6 core biopsies is ideal).

If a site is deemed appropriate for biopsy with minimal risk to the participant by agreement between the investigators and biopsy team, a biopsy will be attempted. The use of imaging to facilitate biopsies will be decided by members of the Interventional Radiology or Radiology team and may include an ultrasound (US), a computer tomography (CT) scan, or a magnetic resonance imaging (MRI) scan. Should a CT scan be needed for biopsy, the number of scans for each procedure will be limited to the minimum number needed to safely obtain a biopsy. Tumor biopsies and local anesthesia will be administered only if they are considered to be of low risk to the participant, as determined by the investigators and/or the interventionist.

Tissue Study Requirements on Treatment Listed in Order of Priority

Test	Institution or commercial entity	Baseline Biopsy (slides)	On Treatment Biopsy (Prior to Cycle 3)
Standard-of-Care Genomic Testing in CLIA Certified Lab	Investigator Choice	Per SOC Guidelines	X
PD-L1 and QIF	Yale Translational Immuno-Oncology	5 slides minimum, 10 slides optimal	5 slides minimum, 10 slides optimal
Next Generation Sequencing with Mutational Load*	Broad Institute	10 slides minimum 20 slides optimal. (RNA later processing if available)	10 slides minimum, 20 slides optimal.

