The baseline assumption is that single agent afatinib yields a response rate of 10% in this setting, and a response rate of 10% or less would not warrant further study. A response rate of 40% or greater would justify further study with a larger sample size. With 10 patients enrolled in cohort A expansion arm, we will declare this combination lacking promise if fewer than 3 patients respond, and potentially worthy of further study if 3 or more patients respond. If the true response rate is 10%, the chance of having 3 or more patients respond is 7%. If the true response rate is 40%, the

chance of having 3 or more patients respond is 83%.

If 3 or more patients respond, the response rate, toxicity, and progression-free survival will be evaluated to decide if larger randomized studies are warranted in this disease. Descriptive summaries will be provided for each of these summary measures (numbers and proportion responding, number and proportion with specific type and grade of toxicities, Kaplan-Meier plot and life-table summary of progression-free survival.) As stated earlier, a “pick the winner” approach between cohort A and cohort B based on toxicity: RR, PFS and changes in PDL1 expression will decide which dosing scheme to take further. It is assumed that a true RR >40% would be sufficient to recommend such development, provided safety and tolerability are also acceptable.

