8.2 Correlative Statistical Analysis Plan

Plasma EGFR-mutant DNA/RNA levels, PDL1 expression by IHC at baseline and in repeat biopsy specimens as well as the other EGFR and immune biomarkers proposed will be evaluated in exploratory manner. A focus is on comparison between changes in PD-L1 expression comparing arm A (concurrent afatinib/MK-3475) and arm B (lead in MK-3475). Descriptive associations with response rate and PFS will be performed. All molecular and other secondary evaluations will be considered for exploratory analyses and in view of the limited sample-size and the exploratory nature of these analyses, any p-values reported will not be adjusted for multiple comparisons, and any such analyses will be stated carefully as being hypothesis-generating.

Standard descriptive methods will be used to summarize the baseline levels and changes in baseline levels will allow us to examine whether observed patterns are consistent with hypothesized patterns. If the combination is not found to have sufficient activity, these patterns may help explain the lack of activity. If sufficient activity is found, then patients who experience an objective response will be compared to those who did not in terms of these correlates.

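### The only on-treatment biopsy precedes Cohort B's first afatinib dose, so tissue PD-L1 change cannot inform a choice between the two completed schemes

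*Combined protocol and SAP*

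**What the plan says.** **Biopsy timing.** Three places agree on one on-treatment biopsy, for every patient, before Cycle 3:

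- Section 6.1, footnote 10: "Repeat biopsy will be performed prior to initiation of cycle 3 (42 days (-7 days".
- Section 7.2.2, where the cut-off is the start of Cycle 3: "two biopsies will be attempted on study: one prior to initiation of study treatment and one after cycle #2 of treatment before initiation".
- Section 4.4.3.2: "Biopsy at Baseline and prior to Cycle #3".

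**Cohort B's afatinib start.** Section 6.1, footnote 9, says that "afatinib will commence in combination with MK-3475 starting with cycle #3". Sections 2.1, 5.1.4 (Table 3 footnote) and 5.2 say the same.

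**Use of PD-L1.** Section 8.1 describes a pick-the-winner "approach between cohort A and cohort B based on toxicity: RR, PFS and changes in PDL1 expression will decide which dosing scheme to take further". Section 8.2 names the measure as "PDL1 expression by IHC at baseline and in repeat biopsy specimens" and states: "A focus is on comparison between changes in PD-L1 expression comparing arm A (concurrent afatinib/MK-3475) and arm B (lead in MK-3475". The same section says that "All molecular and other secondary evaluations will be considered for exploratory analyses".

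**The concern.** Cohort B's scheme is a two-cycle MK-3475 lead-in followed by the combination. Its only on-treatment tissue sample is taken at the end of the lead-in, before the combination starts. A tissue PD-L1 difference between the cohorts may therefore show only that one cohort is taking afatinib and the other is not yet.

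The protocol itself gives a reason to expect such a difference. Section 4.4.1 reports, from preclinical models only, that EGFR-TKI treatment which lowered EGFR pathway activity also lowered PD-L1.

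Section 8.1 makes PD-L1 change one of the deciding inputs and gives it no threshold, weight or favourable direction. Nothing in that section stops an effect of afatinib being present or absent from being read as an effect of concurrent versus sequential scheduling. Section 8.2 gives the same data exploratory status only, so the two sections disagree on what PD-L1 is for.

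**Working it through.** **Inputs**

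- Cycle length: 21 days (5.1.4).
- Cohort A afatinib: from Cycle 1 Day 1 (5.1.4; 6.1, footnote 9).
- Cohort B afatinib: from Cycle 3 Day 1.
- Repeat biopsy: before Cycle 3, at 42 days with a 7-day early window (6.1, footnote 10).
- If cycles are delayed, procedures other than imaging follow the cycle number (6.1, footnote 1).
- Day 1 treatment may move by 3 days either way (5.1.6).

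**The plan's own timing.** Two cycles × 21 days = 42 days. This matches both the six-week lead-in in Section 2.1 and the 42 days in footnote 10. The timetable is internally consistent.

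**Afatinib exposure at the biopsy.** Days on afatinib = biopsy day − afatinib start day, with a floor of zero, counting from the first dose.

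| | Biopsy at day 35 | Biopsy at day 42, before dosing |
|---|---|---|
| Cohort A (starts day 0) | 35 − 0 = 35 | 42 − 0 = 42 |
| Cohort B (starts day 42) | 0 | 42 − 42 = 0 |
| MK-3475 doses given (days 0 and 21) | 2 in each | 2 in each |

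The Cohort A figures assume no pauses in dosing.

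**Sensitivity to drift.** If Cycle 3 starts at day 39 or day 45, a biopsy window ending at that start runs from day 32 to 39 or from day 38 to 45. Cohort B's afatinib exposure stays at 0 in both cases. Longer delays do not change this, because the biopsy is tied to the cycle number.

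**Later tissue.** None is scheduled. A post-progression biopsy appears only as an example of sample coding (7.2.2.3 and 7.2.4.1). It is absent from the flow chart and from the tissue table in 7.2.2.

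**Later blood.** Immune blood is drawn before Cycle 6, within a 3-day early window (6.1, footnote 11). Scheduled combination time by then:

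- Cohort A: 5 × 21 = 105 days (102 to 105 with the window).
- Cohort B: 105 − 42 = 63 days (60 to 63 with the window).

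Blood can therefore describe Cohort B on the combination, but with 42 fewer days of it than Cohort A.

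**The case against.** The strongest reply has four parts.

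1. **The timing is deliberate and useful.** A biopsy at the end of the lead-in isolates what MK-3475 alone does, and Section 8.2 already labels arm B by its lead-in. This stands. Footnote 10 is not an error and needs no change. The fault lies in how Section 8.1 uses the result.

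2. **Section 8.1 does not say tissue.** Section 7.2.1.1 has plasma PD-L1 DNA and RNA quantified, and the requisition form in Appendix 12.6 describes PD-L1 as an expression assay. Plasma is drawn before each cycle under 7.2.1.1. Footnote 11 of the flow chart puts plasma cfDNA draws every two cycles. Either way, samples exist after Cohort B starts afatinib. The plasma reading is possible, but the text favours tissue: Section 3.3 ties PD-L1 change to the tumor microenvironment, Sections 4.4.3.2 and 7.2.3.1 tie it to biopsy immunohistochemistry, and Section 8.2 does likewise. If plasma was meant, Section 8.1 would still have to say so.

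3. **The analysis is declared exploratory and hypothesis-generating.** That is true of Section 8.2, but it does not cancel the deciding role in Section 8.1. It is the reason the two sections need reconciling.

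4. **A team may reasonably weigh lead-in tissue alongside the other inputs, and those inputs lack thresholds too.** Both points are fair. The missing thresholds are a wider weakness of the pick-the-winner sentence. What sets PD-L1 apart is that toxicity, response rate and PFS can all cover the combination period in Cohort B, and tissue PD-L1 cannot.

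**Conclusion.** The concern holds. By schedule, the tissue PD-L1 comparison sets 35 to 42 days of afatinib plus MK-3475 against MK-3475 alone, with two MK-3475 doses in each cohort. It cannot represent Cohort B's completed scheme, yet Section 8.1 as written would let it help select that scheme.

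The reach is limited: one of four selection inputs, and every Cohort B biopsy pair obtained, of which there are at most 10 because biopsies are only attempted. The primary safety objective, the MTD, the Cohort A response rule (3 or more responders of 10), and the toxicity, response and PFS inputs are untouched. This should be corrected, but it does not threaten the trial.

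The conclusion assumes that PD-L1 change in Section 8.1 means the tissue measure in Section 8.2. The Cohort A figure also assumes uninterrupted afatinib; the zero in Cohort B does not depend on that.

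**What to change.** - **Section 8.1:** delete PD-L1 change from the pick-the-winner sentence, so that selection rests on toxicity, response rate and PFS.
- **Sections 3.3 and 8.2:** label the pre-Cycle-3 tissue contrast as *afatinib + MK-3475 versus MK-3475 alone at about 6 weeks*, and keep it exploratory.
- **Section 8.2, RPPA:** state that Cohort B's pre-Cycle-3 sample is a no-afatinib reference and not evidence of target inhibition by afatinib.
- **Section 8.2, blood and plasma:** describe PD-L1 and immune samples taken after Cohort B starts afatinib as exploratory data on that cohort under the combination. Note the unequal exposure (before Cycle 6, about 105 days in A and 63 in B).

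The biopsy schedule stays as it is. The cost is wording in three sections, with no new visit, sample or biopsy. The one loss is that tissue PD-L1 no longer contributes to choosing the scheme. If the team wants PD-L1 to keep some role there, Section 8.1 should at least name the measure and time point, and say that tissue reflects the lead-in only and is supportive.

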7.0 TRIAL PROCEDURES

7.1 Trial Procedures

The Trial Flow Chart - Section 6.0 summarizes the trial procedures to be performed at each visit. Individual trial procedures are described in detail below. It may be necessary to perform these procedures at unscheduled time points if deemed clinically necessary by the investigator.

Furthermore, additional evaluations/testing may be deemed necessary by the Sponsor-Investigator and/or Merck and/or Boehringer-Ingelheim for reasons related to subject safety. In some cases, such evaluation/testing may be potentially sensitive in nature (e.g., HIV, Hepatitis C, etc.), and thus local regulations may require that additional informed consent be obtained from the subject. In these cases, such evaluations/testing will be performed in accordance with those regulations.

7.1.1 Administrative Procedures

7.1.1.1 Informed Consent

The Investigator must obtain documented consent from each potential subject prior to participating in a clinical trial.

7.1.1.1.1 General Informed Consent

Consent must be documented by the subject's dated signature or by the subject's legally acceptable representative's dated signature on a consent form along with the dated signature of the person conducting the consent discussion.

A copy of the signed and dated consent form should be given to the subject before participation in the trial.

The initial informed consent form, any subsequent revised written informed consent form and any written information provided to the subject must receive the IRB/ERC's approval/favorable opinion in advance of use. The subject or his/her legally acceptable representative should be informed in a timely manner if new information becomes available that may be relevant to the subject's willingness to continue participation in the trial. The communication of this information will be provided and documented via a revised consent form or addendum to the original consent form that captures the subject's dated signature or by the subject's legally acceptable representative's dated signature.

Specifics about a trial and the trial population will be added to the consent form template at the protocol level.

The informed consent will adhere to IRB/ERC requirements, applicable laws and regulations and Sponsor-Investigator requirements.

7.1.1.2 Inclusion/Exclusion Criteria

All inclusion and exclusion criteria will be reviewed by the investigator or qualified designee to ensure that the subject qualifies for the trial.

7.1.1.3 Medical History

A medical history will be obtained by the investigator or qualified designee. Medical history will include all active conditions, and any condition diagnosed within the prior 10 years that are considered to be clinically significant by the Investigator. Details regarding the disease for which the subject has enrolled in this study will be recorded separately and not listed as medical history.

7.1.1.4 Prior and Concomitant Medications Review

7.1.1.4.1 Prior Medications

The investigator or qualified designee will review prior medication use, including any protocol-specified washout requirement, and record prior medication taken by the subject within 28 days before starting the trial. Treatment for the disease for which the subject has enrolled in this study will be recorded separately and not listed as a prior medication.

7.1.1.4.2 Concomitant Medications

The investigator or qualified designee will record medication, if any, taken by the subject during the trial. All medications related to reportable SAEs and ECIs should be recorded as defined in Section 7.2.

7.1.1.5 Disease Details and Treatments

7.1.1.5.1 Disease Details

The investigator or qualified designee will obtain prior and current details regarding disease status.

7.1.1.5.2 Prior Treatment Details

The investigator or qualified designee will review all prior cancer treatments including systemic treatments, radiation and surgeries.

7.1.1.5.3 Subsequent Anti-Cancer Therapy Status

The investigator or qualified designee will review all new anti-neoplastic therapy initiated after the last dose of trial treatment. If a subject initiates a new anti-cancer therapy within 30 days after the last dose of trial treatment, the 30 day Safety Follow-up visit must occur before the first dose of the new therapy. Once new anti-cancer therapy has been initiated the subject will move into survival follow-up.

7.1.1.6 Trial Compliance (Medication/Diet/Activity/Other)

The study medication will be given in accordance with the protocol and the instructions of a site investigator.

The appropriate number of afatinib tablets for 3 weeks of treatment will be provided to patients to be self-administered at home.

Patients will be asked to bring the remaining trial medication at the end of each 3 week to the investigator site for a compliance check. The remaining film-coated tablets will be counted by the investigator/site staff and recorded at the investigator site. Discrepancies between the number of tablets remaining and the calculated number of tablets the patients should have taken must be documented and explained. At the end of each 3 week, any remaining medication will be collected. If the patient is eligible for further treatment, a new bottle of study medication must be dispensed.

The investigator can withdraw a patient from the study in the event of serious and persistent non-compliance which jeopardizes the patient's safety or render study results for this patient unacceptable. Patients who do not attend a minimum of 75% of scheduled study visits, unless due to exceptional circumstances, should be discussed with the company supporter and be evaluated for compliance.

7.1.2 Clinical Procedures/Assessments

7.1.2.1 Adverse Event (AE) Monitoring

The investigator or qualified designee will assess each subject to evaluate for potential new or worsening AEs as specified in the Trial Flow Chart and more frequently if clinically indicated. Adverse experiences will be graded and recorded throughout the study and during the follow-up period according to NCI CTCAE Version 4.0 (see Section 12.2). Toxicities will be characterized in terms regarding seriousness, causality, toxicity grading, and action taken with regard to trial treatment.

For subjects receiving treatment with MK-3475 all AEs of unknown etiology associated with MK-3475 exposure should be evaluated to determine if it is possibly an event of clinical interest (ECI) of a potentially immunologic etiology (termed immune-related adverse events, or irAEs). See the separate ECI guidance document in the appendix (Section 12.9) regarding the identification, evaluation and management of potential irAEs.

Refer to section 7.2 for detailed information regarding the assessment and recording of AEs.

